2.2 Background on the investigation

2.2.1 From the research question

Is the application of PRO-231 ophthalmic solution safe and tolerable in clinically healthy subjects?

The importance of the question that precedes this paragraph is that Laboratorios Sophia S.A. de C.V. does not have clinical studies with products identical to the PRO-231 solution, although there are with similar products (different fluoroquinolones and excipients).

2.3 Problem statement

Bacterial conjunctivitis is one of the most common eye infections and it is estimated that it represents up to 1% of consultations at the first level of care, generating a significant economic and social impact, as a result of the interruption of the patient's normal activities, as well as absenteeism from work and/or school. Although it is usually a self-limiting condition, with an average duration of 1 to 2 weeks, empirical treatment with broad-spectrum anti-infective drugs is recommended to shorten the course of the disease, improve patient comfort, decrease transmissibility, promote early return to work or school, and reduce the risk of serious complications that may compromise vision [9][1, 2, 3, 4, 5, 6, 7]

Fluoroquinolones are antibiotics whose usefulness in the area of ophthalmology has already been proven, as they have been used for decades as a treatment and/or prophylaxis for eye infections. Its effectiveness and safety have given this family of drugs a significant place within the therapeutic options of today's ophthalmologist; however, despite being generally well-tolerated drugs with low toxicity, it was decided to compare PRO-231 with VIGAMOXI,® the topical formulation of moxifloxacin 0.5% currently marketed in our country, to verify that its safety and toxicity profile is equal to the latter.

2.4 Rationale for the study

Although eye infections can be considered minor infections, in some cases, they can become complicated and leave irreversible sequelae that can compromise the patient's vision. For this reason it is important to prescribe topical antibiotics for the treatment of eye infections, or as prophylaxis in surgical procedures and eye trauma. An important property of anti-infective drugs is their selective

toxicity, eliminating microorganisms while causing minimal or no adverse reactions to the host. [17, 18] [1]

Moxifloxacin hydrochloride, the active ingredient in PRO-231 ophthalmic solution, is a fourth-generation fluoroquinolone, which has already been approved for use in the treatment of bacterial conjunctivitis and keratitis caused by susceptible strains; and it is already marketed by international ophthalmic product laboratories. It has the advantage of being preservative-free, and in addition, offers broad-spectrum activity, and a moderate to high clinical success rate against common ocular pathogens. In addition to this, thanks to its concentration and its high penetrance to the ocular tissues, it allows a dosing regimen at infrequent intervals, simplifying its administration and making it more convenient for patients. [6, 7, 9, 10]

In our country, this antibiotic formulation is marketed and approved under the name VIGAMOXI® (Alcon Laboratories, Inc. Fort Worth, Texas, USA) for the treatment of bacterial conjunctivitis. Clinical studies are required to evaluate that the safety and tolerability of PRO-231, prepared by Laboratorios Sophia S.A. de C.V., is comparable to that of VIGAMOXI,® and which are the basis of future clinical studies that prove its efficacy. The current commitment of Laboratorios Sophia, S.A. de C.V. is to generate its own information for its products that serves for the pertinent regulatory procedures, and as a scientific basis for their commercialization.

3. Objectives and hypotheses

3.1 Objectives

3.1.1 Main objective:

To evaluate the safety and tolerability of the formulation PRO-231 versus VIGAMOXI,® on the ocular surface of ophthalmologically and clinically healthy subjects.

3.1.2 Specific objectives:

3.1.2.1 Primary

- To assess the safety of PRO-231 ophthalmic solution applied to the ocular surface, in healthy volunteers, versus VIGAMOXI,® by:
 - To compare the incidence of unexpected AEs related to interventions.
 - Incidence of conjunctival hyperemia and/or chemosis between interventions.
 - Changes in the AVMC, evaluated with the Snellen chart, between interventions.
 - Changes in ocular surface integrity using fluorescein staining, using the Oxford scale between interventions.
- To evaluate the tolerability of PRO-231 ophthalmic solution applied to the ocular surface, in healthy volunteers, versus VIGAMOXI,® by:
 - Changes in Eye Comfort Index (JI) score between interventions.

3.1.2.2 Secondary

- To assess the safety of PRO-231 ophthalmic solution applied to the ocular surface, in healthy volunteers, versus VIGAMOXI,® by:
 - Incidence of expected and intervention-related AEs (excluding conjunctival hyperemia and/or chemosis).
- To evaluate the tolerability of PRO-231 ophthalmic solution applied to the ocular surface, in healthy volunteers, versus VIGAMOXI,® by:
 - Presence of ocular symptoms (burning, foreign body sensation, pruritus and tearing) between interventions.

3.2 Study hypothesis

H0: PRO-231 ophthalmic solution has a similar safety and tolerability profile as VIGAMOXI® in clinically healthy subjects.

$$H_0: ST_A = ST_B \text{ o } ST_A - ST_B = 0$$

H1: PRO-231 ophthalmic solution does not have a similar safety and tolerability profile as VIGAMOXI® in clinically healthy subjects.

$$H_1: ST_A \neq ST_B \text{ o } ST_A - ST_B \neq 0$$

Operational definition of similarity: To reject H0, the p-value in the primary variables must be ≤ 0.05 and the 95% CI of this difference must not include zero. Both conditions for hypothesis testing (p-value and 95% CI) must be met, otherwise the result will be interpreted as "**absence of evidence**", not as "**evidence of absence**".

4. Study design

4.1 Study Overview

Phase I clinical study, controlled, comparative, parallel-group, single-blind, single-center.

4.2 Rationale for the study design

The design of the study (clinical trial) is considered the highest standard of data quality when seeking to explore the effect of an intervention. The drug development phase (phase I) corresponds to the objective of the study, which is to evaluate safety and tolerability, so the intervention time is short and the sample size required is smaller than that of an efficacy clinical trial.

Although this is a comparative study with two intervention groups, only the principal investigator and the person responsible for the statistical analysis will be blinded, because the primary packaging of the comparator cannot be modified to resemble the product under investigation. Despite this, the secondary packaging for the products will be the same and the researcher will not know the allocation.

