7.3 Assignment of treatment

The assignment/randomization of the treatment will be carried out centrally using a validated electronic system from an external provider, previously evaluated and authorized by Laboratorios Sophia S.A. de C.V. There are two treatment groups. Participants will be randomized in a 1:1 ratio to treatment with PRO-231 or VIGAMOXI.® Having the same probability of being assigned to one or the other treatment. After signing the FCI, the subject will receive a participant number with which all their information will be encrypted pseudonymity during collection and completely anonymized during analysis. The generation will be carried out by a third party, authorized by Laboratorios Sophia, S.A. de C.V., through its electronic system, through a list of random numbers generated by software (SAS Institute Inc, Cary, NC, USA). The information pertaining to this third party will be on file. Only the principal investigator and the person responsible for the statistical analysis will be blinded, because the primary packaging of the comparator cannot be modified to resemble the product under investigation. Despite this, the secondary packaging for the products will be the same and the researcher will not know the allocation. IP will be identified by means of labels in accordance with current and applicable regulations, which must contain at least:

- Sponsor's name, address, and phone number.
- Dosage form and route of administration.
- Number of doses.
- Batch number.
- Legend "Exclusively for clinical studies".
- Expiration date.

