7.4.4.3 Ocular symptomatology

The subject will be questioned directly about the presence in general (since the last visit) of the following symptoms: burning, foreign body sensation, pruritus, tearing.

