7.4.4.7 Eye Comfort Index

It is a questionnaire designed to measure ocular surface irritation with Rasch analysis to produce estimates on a linear interval scale (ratings: 0-100). Similar to the index for ocular surface diseases, the ocular comfort index (ICO) assesses symptoms. The ICO contains 8 items (one positive and eight negative) that focus on discomfort associated with ocular surface alterations. Each of these questions has two parts, which separately inquire about the frequency and severity of symptoms. [\[43\]](#) See attachment [16.4 Eye Comfort Index \(JI\)](#)

At the baseline visit and final visit, the evaluator will deliver the questionnaire to the subject and allow the subject to answer it calmly without any pressure and/or coercion, only assisting him if he has difficulty understanding any of the questions.

As it is a subjective measurement scale according to the subject's symptomatology, variations in the ICO cannot be managed as AEs.

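### The reason given for leaving subjects unblinded (bottles that do not look alike) does not rule out concealing the product name, and the tolerability outcomes are self-reported

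*Combined protocol and SAP*

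**What the plan says.** Section 4.1 describes the trial as "Phase I clinical study, controlled, comparative, parallel-group, single-blind, single-center". Section 4.2 says that "only the principal investigator and the person responsible for the statistical analysis will be blinded", and gives one reason: "because the primary packaging of the comparator cannot be modified to resemble the product under investigation". Section 7.3 repeats the reason and adds: "Despite this, the secondary packaging for the products will be the same and the researcher will not know the allocation". The common outer packaging protects the investigator. Nothing comparable is described for the bottle that the subject uses for seven days.

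On allocation, section 7.3 states: "Participants will be randomized in a 1:1 ratio to treatment with PRO-231 or VIGAMOXI". On labels it states: "IP will be identified by means of labels in accordance with current and applicable regulations, which must contain at least". The list that follows covers the sponsor's details, dosage form and route, number of doses, batch number, a clinical-studies legend and expiry date. The product name is not among these minimum items.

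The only primary tolerability variable is the change in ICO score (section 7.4.1.2), from a questionnaire that the subject completes. Section 7.4.4.7 explains why ICO changes are not handled as adverse events: "As it is a subjective measurement scale according to the subject's symptomatology". The secondary tolerability variable is equally the subject's account. Section 7.4.4.3 says: "The subject will be questioned directly about the presence in general (since the last visit) of the following symptoms", namely burning, foreign body sensation, pruritus and tearing, each answered as absent or present.

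**The concern.** Making two containers look alike serves people who can compare them. A subject here is assigned to one product and may not enrol twice (section 5.1.2), so the main thing to hide is which product it is, not every difference between the containers. The protocol goes straight from the bottles not being identical to the subject not being blinded, without considering that intermediate step.

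The blind therefore covers the person who grades the eye signs but not the person who supplies all the tolerability data. A subject who knows that the drop is experimental, or that it is an established brand, may report discomfort differently. Section 10.3.1 then turns the comparison into a verdict: a significant difference is read as the products being different, and a non-significant one as their being similar. Expectation could push the ICO towards either reading, and no planned analysis could separate it from a real effect.

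**Working it through.** **1. What the stated reason covers.**

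| Item | What the documents give | Section |
|---|---|---|
| Products per subject | One, allocated 1:1, no re-entry | 7.3, 5.1.2 |
| PRO-231 container | White low-density polyethylene, 5 mL | 6.1.1 |
| Comparator container | Natural low-density polyethylene with its own dispensing cap, 5 mL | 6.1.4 |
| Solutions | Yellow; greenish-yellow | 6.1.1, 6.1.4 |
| Current users of topical eye drugs | Excluded; no look-back on past use | 5.1.2 |
| Over-label, sleeve or other cover on the bottle | None described | 4.2, 7.3 |
| Study label | Required; minimum list has no product name | 7.3 |

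The container differences support the statement that the bottles cannot be matched. They do not show that the name cannot be covered.

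**2. Which outcomes are exposed.** The ICO and the four symptoms come directly from the subject. Hyperemia, chemosis and fluorescein staining are graded by the blinded investigator. Visual acuity needs the subject's responses. Adverse events are judged by the investigator but partly elicited by questioning. The exposure falls mainly on the tolerability outcomes.

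**3. The plan's own numbers.** Section 10.1.2 gives 17 per arm, raised by 10% to 19: 17 × 1.10 = 18.7, and 17 / 0.90 = 18.9; both round up to 19. The 17 itself is recovered from the two-proportion formula with both variance terms, 6/62 = 0.0968 against 0.50, two-sided 0.05, and 80% power (an assumption, since the plan states no power):

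(0.0968 × 0.9032 + 0.25) × ((1.960 + 0.842) / 0.4032)² = 0.3374 × 48.27 = 16.29, rounded up to 17.

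Whether 6 events or 3 patients was the right count is a separate matter. I use 17 as the evaluable number after the planned losses, because primary variables are analysed per protocol (section 10.3.2.1), and 19 as the number with no losses.

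**4. Illustration of the bias.** Assumptions: no true ICO difference, a t-test for independent groups, two-sided 0.05, and a between-arm reporting shift of b standard deviations. The documents give neither b nor an ICO standard deviation, so b is assumed over a range. The test statistic is noncentral t with df = 2n − 2 and noncentrality b × √(n/2). The probability of rejection is P(|T| > critical value).

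For n = 17: df = 32, critical value 2.037, √(17/2) = 2.915.

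| Assumed shift b | Noncentrality, n = 17 | P(false difference), n = 17 | P(false difference), n = 19 |
|---|---|---|---|
| 0 | 0 | 0.050 | 0.050 |
| 0.2 SD | 0.583 | 0.087 | 0.092 |
| 0.3 SD | 0.875 | 0.136 | 0.147 |
| 0.5 SD | 1.458 | 0.293 | 0.323 |

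A shift in the opposite direction to a true difference would offset it by the same amount.

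**The case against.** The protocol declares the trial single-blind, gives its reason, and blinds the examiner and the analyst. Most of the listed primary variables are graded or judged by that blinded examiner. Both arms receive moxifloxacin 0.5%, so the expectation contrast may be weaker than between drug and placebo, and nothing in the documents shows any non-zero bias. Sample size is the larger limitation on the ICO: at 17 per arm, true differences of 0.2, 0.3 and 0.5 SD would be detected only 9%, 14% and 29% of the time even with perfect masking. All of this stands. It limits the weight of the point without supplying the missing reason.

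A reader might infer that covering the brand would fully blind the subjects. The documents do not support that. The containers, the cap and the solution colour differ; the comparator is marketed in the country and named in the study title; and section 5.1.2 excludes current users of eye drops without excluding past use. Some subjects could still recognise the product.

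A reader might also infer that the label list in section 7.3 permits the product name to be omitted, or that the trade label is known to remain visible. Neither is stated. The list is a minimum under applicable regulations, and the protocol is silent on what happens to the manufacturer's label. It does declare subjects unblinded and describes no concealment.

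Finally, labels with identical content would conflict with section 7.3, which requires batch number and expiry date; these will ordinarily differ between two manufacturers' products. Limiting what subjects are told would touch consent (sections 11.4.1 and 11.4.3). The fix has to respect both.

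**Conclusion.** The point holds in a limited form. Unlike bottles are the only reason given for not blinding subjects, and that reason does not rule out concealing the product name from someone who handles one product. No section describes an attempt, and every tolerability outcome is self-reported.

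The size and direction of any resulting bias are unknown. The rise from 5% to about 9% to 29% is conditional on an assumed shift of 0.2 to 0.5 SD, a t-test and 17 evaluable subjects per arm; it is not an estimate for this trial. It would go too far to conclude that the ICO comparison is invalid, or that the examiner-graded safety outcomes are compromised to the same degree. This is an inexpensive improvement to the design, not the correction of a wrong figure. Masking subjects changes neither sample size nor alpha.

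**What to change.** Apply the study label that section 7.3 already requires as an opaque over-label of the same format on both bottles, covering the manufacturer's name and brand. Show batch number and expiry date as regulations require, coded if that is permitted. Have the group that prepares the common secondary packaging apply it.

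Amend sections 4.1, 4.2 and 7.3 to say that product identity is concealed from subjects as far as feasible. Submit any related subject-facing wording to the ethics committee. At the final visit, record whether the subject recognised the product, so that the report can say how far the masking worked.

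The cost is label design, a packaging step, a protocol amendment and any consent wording that follows from it. Container, dosing, sample size and analysis are unchanged. The downside is that masking is partial, for the reasons above. The sponsor must first confirm that over-labelling the comparator is permitted. If it is not, the protocol should say so and state unblinded self-report as a limitation on the ICO and symptom conclusions.

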4.3 Expected duration of the study

The total duration of the study, from the first subject's first visit to the preparation of the final report, is estimated to be 5 to 6 months.

4.4 Duration of the subject in the study/treatment

The approximate duration of each subject in the study is up to 13 days.

5. Study population

5.1 Eligibility Criteria

5.1.1 Inclusion criteria

- Have the ability to voluntarily give their signed informed consent.
- Ophthalmologically and clinically healthy subjects.
- Be able and willing to comply with scheduled visits, treatment plan, and other study procedures.
- Age 18 to 45 years.
- Both sexes.
- Women of childbearing potential must ensure continued use (initiated \geq 30 days prior to signing the CRF) of the use of a hormonal contraceptive method or IUD during the study period.
- AVMC of 20/30 or better in both eyes.
- Corneal staining \leq grade I on the Oxford Scale.
- Have an intraocular pressure \geq 10 and \leq 21 mmHg.

5.1.2 Exclusion criteria:

- History of hypersensitivity to fluoroquinolones or any of the components of the PI.
- Be a user of topical ophthalmic medications of any pharmacological group.
- Be a user of medicines by any other means of administration.
- History of eye surgery in the last 6 months.
- Wearing contact lenses for less than two weeks prior to the start of the study, and during the study intervention period.
- For women: being pregnant, breastfeeding, or planning to become pregnant within the study period.
- Have participated in any investigational clinical study 30 days prior to inclusion in this study.
- Have previously participated in this same study.
- History of any chronic-degenerative disease, including Diabetes Mellitus or Systemic Arterial Hypertension.
- Known diagnosis of liver or heart disease.
- Have active inflammatory or infectious disease at the time of study entry.
- Have unresolved injuries or trauma at the time of study entry.
- Having undergone surgical, non-ophthalmologic procedures within the past 3 months.
- Have received doses of vaccine against the Influenza virus or Coronavirus, 7 days prior to the inclusion of this study, or plan to receive it during the intervention of the same.

- Be or have an immediate family member (e.g., spouse, parent/legal guardian, sibling, or child) who is employed by the research site or sponsor, and who is directly involved in this study.
- Positive smoking (specified as cigarette smoking regardless of quantity and frequency, 4 weeks prior to study inclusion and during the study intervention period).
- Positive alcoholism (specified as the consumption of alcoholic beverages, regardless of quantity and frequency, 72 hours prior to the inclusion of the study and during the study intervention period).

5.2 Criteria for elimination and/or substitution of subjects

5.2.1 Elimination Criteria

- Withdrawal of the consent form under information.
- Presentation of a serious adverse event, whether or not related to the PIs, that, in the judgment of the PI and/or the sponsor, could affect the patient's ability to continue with study procedures safely.
- Non-tolerability or hypersensitivity to any of the compounds used during the tests (fluorescein, tetracaine).
- No tolerability or hypersensitivity to any of the investigational drugs.
- Adherence < 80% determined by the subject's diary and corroborated by the final weight of the PI with respect to the initial weight.

5.2.2 Substitution of subjects

The sponsor may decide to replace subjects who withdraw their FCI or those who have loss of follow-up, until the necessary sample size is completed.

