5.5 Procedure in case of loss of follow-up

For this protocol, loss of follow-up is defined as those subjects who were assigned the PI, who at some point were active subjects of the study, but their final evaluation could not be completed.

In the event that the subject does not terminate their participation due to withdrawal of consent or major deviation, the last visit, in which their withdrawal was determined, will be considered their final visit. Subjects who are removed due to the presence of AEs will continue with the follow-up that is defined until the closure of their AE.

In cases where the participating subject does not attend their appointment, the research center must make a call to find out the reason and will try to make a new appointment within the established window period or an unscheduled appointment. In the event that it is not possible to make an appointment, the subject will be considered as loss of follow-up and will be asked about the presence of adverse events and the reason for leaving the study, as minimum data.

A loss of follow-up <20% is considered not to be a problem for the validity of the results obtained.
[20, 21]

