6.1.3 Treatment with the investigational product

The product under investigation will be delivered at the conclusion of the baseline visit. The subject under investigation will begin the application the next day (day 1) by administering one drop every 6 hours, applying a total of one drop three times a day to the right eye during the 7 days of application.

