10.1.2 Size Calculation

PRO-231 ophthalmic solution is expected to be safe in its ophthalmic application as it presents an incidence of AE similar to that presented by VIGAMOXI.®

On this basis, a sample of 17 ophthalmologically and clinically healthy subjects was estimated. This value increased by 10% considering possible losses. Based on this consideration, 19 subjects per arm (38 subjects in total) are required to provide one eye (OD) to respond to the primary objective of the study.

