10.3.2 Safety and tolerability analysis

10.3.2.1 Analysis for Primary Variables

The analysis of the primary outcome variables of safety and tolerability will be carried out in the per-protocol population (PP), defined as any subject with an adherence $\geq 80\%$ determined by the subject's diary and corroborated by the final weight of the research product to which it was assigned (PRO-231 or VIGAMOXI)[®] with respect to its initial weight. and that they conclude their participation without deviations from the study protocol.

The Shapiro-Wilk test (S-W) will be used to determine if the distribution is normal in the data obtained in each study group ($p>0.05$). If the normality in the distribution of the data is verified, to rule out differences between groups, the Student's t-statistic will be used for independent groups, while intragroup differences will be analyzed with the Student's t-test for repeated measures.

In case of $p < 0.05$ in S-W, the statistical analysis to rule out differences between groups will be performed by means of the Mann-Whitney U test for quantitative variables, while intragroup differences will be performed by Wilcoxon's rank test.

For qualitative variables, Pearson's X² (Chi-square) or Fisher's exact test will be used in expected values less than 5. Dichotomous variables will be analyzed by the McNemar test when applicable.

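### Replacement of dosed subjects who withdraw or are lost is permitted, and with a completers-only primary analysis it can mask discomfort-driven attrition

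*Combined protocol and SAP*

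**What the plan says.** Section 5.2.2 gives the rule: "The sponsor may decide to replace subjects who withdraw their FCI or those who have loss of follow-up" (FCI is the consent form). It allows this up to the point where the required number is reached. It sets no condition about dosing. It does not say which arm a replacement joins or how a replaced subject is reported.

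Section 5.5 defines the second replaceable group as people who already had a product assigned and had taken an active part, "but their final evaluation could not be completed". Sections 6.1.3 and 6.1.6 start dosing the day after the baseline visit, so most subjects in either group will have used the drops.

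Section 5.2.1 lists a separate ground for elimination, "No tolerability or hypersensitivity to any of the investigational drugs", which section 5.2.2 does not name as replaceable.

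On analysis, section 10.3.2.1 puts all primary variables in the per-protocol set: adherence of at least 80% and participation concluded without deviations. Section 10.3.2.2 uses everyone with at least one dose, but only for the secondary variables. Section 10.4.1 provides no imputation. The decision table in section 10.3.1 reads a non-significant result with a 95% CI that includes zero as similarity.

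On numbers, section 10.1.2 estimates 17 subjects and then states: "This value increased by 10% considering possible losses", which gives 19 per arm and 38 in total.

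**The concern.** In a tolerability trial, leaving because the drops are unpleasant is information about the product. Under this plan such a subject contributes nothing to the primary comparison, and the subject who takes the place counts only by completing with adequate adherence. Because similarity is concluded from a non-significant difference, anything that removes affected subjects pushes towards the favourable conclusion. The party that decides on replacement is the sponsor. Sections 4.2 and 7.3 blind only the principal investigator and the person responsible for the statistical analysis; nothing says that whoever decides on replacement is blind to the arm.

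The measurements make such a departure easy to miss. Burning, foreign body sensation, pruritus and tearing are not treated as adverse events (section 7.4.4.3.4), nor are changes in the comfort index (section 7.4.4.7). Hyperemia becomes an adverse event only from grade 3 (section 7.4.4.1). The comfort index, the only primary tolerability variable, is taken only at baseline and the final visit (section 7.6.2). A subject who stops attending because the drops sting may leave no adverse event and no comfort-index change.

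**Working it through.** **1. The plan's own figure.** From 17 evaluable subjects with a 10% allowance, 17/0.9 = 18.9 and 17 × 1.1 = 18.7. Both round up to 19, as stated. The allowance is 19 − 17 = 2 losses per arm.

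**2. How far the allowance goes.** Assume each subject is lost, for any cause, with probability 10%, independently. For 19 subjects:
- P(2 or more losses) = 1 − 0.9^19 − 19 × 0.1 × 0.9^18 = 1 − 0.135 − 0.285 = 0.58.
- P(3 or more losses, leaving fewer than 17) = 0.29.
- P(at least one of two arms below 17) = 1 − (1 − 0.295)² = 0.50.

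The 58% is the chance of two or more losses of any kind in an arm. It is not the chance of discomfort-driven replacement.

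**3. Separating the per-protocol rule from replacement.** Assume 5 of 19 on PRO-231 and 0 of 19 on the comparator have a problem, and that all five affected subjects leave.

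| Analysis | PRO-231 | Comparator | Fisher p, two-sided |
|---|---|---|---|
| All dosed subjects | 5/19 | 0/19 | 0.046 |
| Per-protocol, no replacement | 0/14 | 0/19 | 1 |
| Per-protocol, five replaced by unaffected completers | 0/19 | 0/19 | 1 |

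The events disappear at the second row, before anyone is replaced. Replacement makes the zero look firmer: the exact 95% upper limit for zero events is 1 − 0.025^(1/n), which is 23.2% for n = 14 and 17.6% for n = 19. It also removes the visible shortfall of five.

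**4. A milder case.** Only one of the five affected subjects leaves.

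| Analysis | PRO-231 | Two-sided p | One-sided p |
|---|---|---|---|
| All dosed subjects | 5/19 | 0.046 | 0.023 |
| Per-protocol, no replacement | 4/18 | 0.046 | 0.046 |
| Per-protocol, replaced by an unaffected completer | 4/19 | 0.105 | 0.053 |

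The comparator is 0/19 throughout. One replaced subject can move the result across 0.05. The two-sided jump at the last step is mostly discreteness: one-sided, C(18,4)/C(37,4) = 3060/66045 = 0.046 becomes C(19,4)/C(38,4) = 3876/73815 = 0.053, so the larger shift comes from removing the affected subject.

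**5. Expected size.** Let p be the true problem rate and f the share of affected subjects who leave. Assume unaffected subjects stay. The rate among completers is p(1 − f)/(1 − pf), with or without replacement. Without replacement, 19(1 − pf) completers are expected; with it, 19/(1 − pf) subjects are dosed to fill the arm.

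| p | f | Rate among completers | Completers, no replacement | Dosed to fill 19 |
|---|---|---|---|---|
| 20% | 25% | 15.8% | 18.1 | 20.0 |
| 20% | 50% | 11.1% | 17.1 | 21.1 |
| 30% | 50% | 17.6% | 16.2 | 22.4 |

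All values of p and f are assumptions; the documents give none.

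**The case against.** The strongest reply is that this is a problem of the analysis set. That largely stands: a dosed leaver is outside the primary analysis whether replaced or not, and rewording section 5.2.2 alone would recover no lost event.

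Four stronger readings are tempting, and the documents do not support them.

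- *The plan swaps intolerant subjects for tolerant ones.* Section 5.2.2 says the sponsor may replace, and names only consent withdrawal and loss to follow-up. Elimination for intolerance is separate and not listed as replaceable. What remains is the subject who leaves for discomfort but is recorded as withdrawn or lost; section 5.2.2 does not make replacement depend on the reason for leaving.
- *Replaced subjects disappear from the trial.* The safety set in section 10.3.2.2 includes anyone dosed, whatever their adherence, so it already keeps them for the secondary variables, ocular symptoms among them. Section 5.5 asks lost subjects about adverse events and the reason for leaving, and follows subjects removed for adverse events to closure. Neither provision reaches the primary comparison, and section 10.3.2.2 applies only where the necessary measurements exist.
- *The 10% allowance makes replacement unnecessary.* It covers about two losses per arm but does not guarantee 17, as step 2 shows. The closing words of section 5.2.2 can also be read as topping up only when needed.
- *A significant difference would be erased.* The counts are invented, and no primary variable is a withdrawal proportion. At 10% loss, five or more losses in an arm has probability 3.5%. A 2/19 against 0/19 split has p = 0.49, so replacing those two changes no significance decision.

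**Conclusion.** The point holds in a limited form. The plan permits, but does not require, replacement of dosed subjects, and its primary analyses count adherent completers only. Together these let a discomfort-driven departure recorded as withdrawal or loss leave the primary comparison while the arm is refilled. The direction favours similarity.

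The bias in the event rate belongs to the per-protocol rule. Replacement adds a restored denominator, apparent precision and concealed attrition. How large the effect would be depends on assumed values: a true 20% problem rate with half of the affected subjects leaving would show as 11.1%. The documents give no basis for saying how often this would happen. The change is worth making because it is inexpensive and affects the primary conclusion.

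**What to change.** Change sections 5.2.2 and 10.3.2.1 together.

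- **Section 10.3.2.1:** analyse the primary safety variables in all subjects with at least one dose, in the assigned arm, with all data up to withdrawal. Keep the per-protocol analysis as supporting.
- **Section 5.2.2:** limit replacement to subjects who were assigned but never instilled a dose. Failing that, state that a replacement is added to, and never substitutes for, a dosed subject, and say how the replacement's arm is determined.
- **Reporting:** list withdrawals, losses, replacements and reasons by arm, and present them with the tolerability results.

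The comfort-index change still needs a post-baseline value, so for subjects who leave without one the by-arm listing is the main remaining evidence.

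The cost is protocol wording and one additional table. The planned 19 per arm need not change. The downside is that an arm may end with fewer than 17 completers, with probability about 0.29 per arm if losses run at 10%.
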